11.0 Treatment Evaluation/Measurement of Effect

Various measurement options exist that are being done in patients with liver cancer and liver metastases and immunotherapy that are of value to consider. These include:

- RECIST 1.1
- iRECIST
- mRECIST

11.1 Treatment evaluation using mRECIST as well as iRECIST Guidelines

The first scan prior to treatment initiation will be performed; the next scan will be then performed at the end of treatment visit. It will then continue every 8-12 weeks per physician discretion until disease progression is confirmed or withdrawn of consent. (See Section 4.0).

Disease progression for this protocol is defined as meeting the mRECIST as well as iRECIST criteria detailed in appendix VI.

11.2 Definitions of measurable and non-measurable disease

11.21 Target Lesion Response mRECIST

- **Complete Response** - Disappearance of any intratumoral arterial enhancement in all target lesions.
- **Partial Response** - At least a 30% decrease in the sum of the diameters of viable (enhancement in the arterial phase) target lesions, taking as reference the baseline sum of the diameters of target lesions.
- **Progressive Disease** – An increase of at least 20% in the sum of the diameters of viable (enhancing) target lesions, taking as reference the smallest sum of the diameters of viable (enhancing) target lesions recorded since treatment started.
- **Stable Disease** – Any cases that do not qualify for either partial response or progressive disease.

11.22 Nontarget Lesion Response

- **Complete Response** - Disappearance of intratumoral arterial enhancement in nontarget lesions.
- **Incomplete Response/Stable Disease** - Persistence of intratumoral arterial enhancement in 1 or more nontarget lesions.
- **Progressive Disease** – Appearance of 1 or more new lesions and/or unequivocal progression of existing nontarget lesions.

Special recommendations for assessment of tumor response in nontarget lesions in patients with HCC and cirrhosis can be made regarding the following:

- **Portal vein thrombosis:** Malignant portal vein thrombosis should be considered a nonmeasurable lesion due to the difficulty in performing consistent measurements of the malignant thrombus during the course of treatment.
- **Porta hepatis lymph node:** Lymph nodes detected at the porta hepatis can be considered as malignant if the lymph node short axis is at least 20 mm.
- **Pleural effusion and ascites:** Cytopathologic confirmation of the neoplastic nature of any effusion (particularly ascites) that appears or worsens during treatment is required when the measurable tumor has met criteria for response or stable disease.

11.23 Appearance of New Lesions

In the assessment of tumor progression, the following concepts have been adopted by mRECIST for HCC:

- A newly detected hepatic nodule will be classified as HCC, and therefore will be declared as evidence of progression, when its longest diameter is at least 1 cm and the nodule shows the typical vascular pattern of HCC on dynamic imaging (i.e., hypervascularization in the arterial phase with washout in the portal venous or late venous phase).
- Liver lesions larger than 1 cm that do not show a typical vascular pattern can be diagnosed as HCC by evidence of at least 1-cm-interval growth in subsequent scans. The date of progression is defined as the time a new lesion was first detected by imaging techniques, even if strict criteria were fulfilled only on subsequent radiologic testing.

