3.1 Inclusion Criteria

- 3.1.1 Age \geq 18 years
- 3.1.2 Histological or cytological confirmation of colorectal cancer with metastasis to the liver. Mismatch repair or microsatellite instability status of the tumor needs to be known. Tumors need to be mismatch repair proficient (for mismatch repair deficient tumors immunotherapy is already approved).
- 3.1.3 Patient must have at least 1 liver lesion measurable as defined in [Section 11.0](#).
- 3.1.4 Must have liver metastases and be appropriate for treatment with Y90-RE therapy as determined by the treating medical oncologist and interventional radiologist/oncologist, and nuclear medicine physician(s).

NOTE: the goal of therapy is safety and parenchymal sparing. Typically, since the treatment is personalized, the goal is to have at least 30% liver parenchymal sparing post treatment.

- 3.1.5 Must have a metastatic focus amendable to biopsy. It is permissible to use same or alternative lesion for biopsy for assessment for tumor response and changes in microenvironment (mandatory pre- and post-Y90-RE biopsy).
- 3.1.6 **At least 2 but no more than 3 lines of therapy** allowed in metastatic setting. These include at least treatment with a fluoropyrimidine, oxaliplatin, and/or irinotecan-based

therapy and an anti-EGFR therapy if RAS wild-type (unless deemed intolerant or not suitable by the treating oncologist), with or without an anti-VEGF therapy.

NOTE: adjuvant and/or maintenance chemotherapy does not count as an additional line of therapy. (Patients with more than 3 lines of therapy are at risk for liver disease from prior systemic therapies and would not be reasonable candidates for Y90-RE).

- 3.1.7 At least a 4-week gap between anti-VEGF therapy and the IR Tc-99m labelled MAA eligibility mapping
- 3.1.8 ECOG Performance Status (PS) 0 or 1 ([Appendix I](#)).
- 3.1.9 Negative *serum* pregnancy test done ≤ 7 days prior to registration, for persons of childbearing potential only.

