11.24 Overall Response Assessment

In mRECIST for HCC, identical to conventional RECIST v1.1, overall subject response is a result of the combined assessment of both intra- and extrahepatic target lesions, non-target lesions, and new lesions.

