- Cytology and histology can be used to differentiate between PR and CR in rare cases (e.g., after treatment to differentiate between residual benign lesions and residual malignant lesions in tumor types such as germ cell tumors).

A.3 Baseline documentation of “Target” and “Non-Target” lesions

- All measurable lesions up to a maximum of five lesions per organ and 10 lesions in total, representative of all involved organs should be identified as target lesions and recorded and measured at baseline.
- Target lesions should be selected on the basis of their size (lesions with the longest diameter) and their suitability for accurate repeated measurements (either by imaging techniques or clinically).
- A sum of the longest diameter (LD) for all target lesions will be calculated and reported as the baseline sum LD. The baseline sum LD will be used as reference by which to characterize the objective tumor.
- All other lesions (or sites of disease) should be identified as non-target lesions and should also be recorded at baseline. Measurements of these lesions are not required, but the presence or absence of each should be noted throughout follow-up.

A.4 Response Criteria

Evaluation of target lesions

Complete Response (CR):	Disappearance of all target lesions
Partial Response (PR):	At least a 30% decrease in the sum of the LD of target lesions, taking as reference the baseline sum LD
Progressive Disease (PD):	At least a 20% increase in the sum of the LD of target lesions, taking as reference the smallest sum LD recorded since the treatment started or the appearance of one or more new lesions
Stable Disease (SD):	Neither sufficient shrinkage to qualify for PR nor sufficient increase to qualify for PD, taking as reference the smallest sum LD since the treatment started

Evaluation of non-target lesions

Complete Response (CR):	Disappearance of all non-target lesions and normalization of tumor marker level
Incomplete Response / Stable Disease (SD):	Persistence of one or more non-target lesion(s) or/and maintenance of tumor marker level above the normal limits
Progressive Disease (PD):	Appearance of one or more new lesions and/or unequivocal progression of existing non-target lesions. Although a clear progression of “non target” lesions only is exceptional, in such circumstances, the opinion of the treating physician should prevail and the progression status should be confirmed later on by the review panel (or study chair).

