IV.C. Modified Evaluation Criteria in Solid Tumors (mRECIST) Quick Reference

Modified RECIST for hepatocellular carcinoma

Response assessment	
Target lesions	
CR	Disappearance of all target lesions or disappearance of any intratumoral arterial enhancement in all target lesions.
PR	At least 30% decrease in the sum of the diameters of viable (enhancing) target lesions, taking as a reference the baseline sum of the diameters of target lesions.*
PD	Any increase of at least 20% in the sum of the diameters of viable target lesions, taking as a reference the smallest sum of the diameters of viable (enhancing) target lesions recorded since treatment started.*
SD	Any cases that do not qualify for either PR or PD.
Non-target lesions	
Malignant portal vein thrombosis	Should be considered a nonmeasurable lesion.
Lymph nodes	If detected at the porta hepatis, should be considered malignant if the short axis dimension is ≥ 2.0 cm.
Pleural effusions and ascites	Emergence of, or increase in, ascites is common during the course of treatment of a cirrhotic patient, and may reflect worsening of the underlying chronic liver disease and be unrelated to cancer progression. The same is true of pleural effusions. Cytopathologic confirmation of the neoplastic nature of any effusion that appears during treatment is required when the measurable tumor has met criteria for response or SD.
New lesions	A newly detected hepatic nodule is classified as hepatocellular carcinoma (and declared evidence of progression) when its longest diameter is at least 1 cm and the nodule has a typical vascular pattern on dynamic imaging (hypervascular in arterial phase with washout in the portal venous or late venous phase). Liver lesions >1 cm that do not show a typical vascular pattern can be diagnosed as hepatocellular carcinoma if there is at least 1 cm internal growth on subsequent scans.

RECIST: Response Evaluation Criteria In Solid Tumors; CR: complete response; PR: partial response; PD: progressive disease; SD: stable disease.

* Enhancement in the arterial phase reflects viable tumor tissue.

Adapted from: Lencioni R, Llovet JM. Modified RECIST (mRECIST) assessment for hepatocellular carcinoma. *Semin Liver Dis* 2010; 30:52.

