Women ≥50 years of age would be considered post-menopausal if they have been amenorrhoeic for 12 months or more following cessation of all exogenous hormonal treatments, had radiation-induced menopause with last menses >1 year ago, had chemotherapy-induced menopause with last menses >1 year ago.

Highly effective methods of contraception, defined as one that results in a low failure rate (ie, less than 1% per year) when used consistently and correctly are herein described. Note that some contraception methods are not considered highly effective (e.g. male or female condom with or without spermicide; female cap, diaphragm, or sponge with or without spermicide; non-copper containing intrauterine device; progestogen-only oral hormonal contraceptive pills where inhibition of ovulation is not the primary mode of action [excluding Cerazette/desogestrel which is considered highly effective]; and triphasic combined oral contraceptive pills).

Highly effective methods

Copper T intrauterine device

Levonorgestrel-releasing intrauterine system (e.g., Mirena®)^a

Implants: Etonogestrel-releasing implants: e.g. Implanon® or Norplant®

Intravaginal: Ethinylestradiol/etonogestrel-releasing intravaginal devices: e.g. NuvaRing®

Injection: Medroxyprogesterone injection: e.g. Depo-Provera®

Combined Pill: Normal and low dose combined oral contraceptive pill

Patch: Norelgestromin/ethinylestradiol-releasing transdermal system: e.g. Ortho Evra®

Minipillc: Progesterone based oral contraceptive pill using desogestrel: Cerazette® is currently the only highly effective progesterone-based

Blood donation

Patients should not donate blood while participating in this study of Durvalumab with Y90-RE for at least 90 days following the last infusion of durvalumab.

Appendix VI: TheraSpheres Prescribing Information**Package Insert****TheraSphere® Yttrium-90 Glass Microspheres****Humanitarian Device.**

Authorized by Federal Law for use in radiation treatment or as a neoadjuvant to surgery or transplantation in patients with unresectable hepatocellular carcinoma (HCC) who can have placement of appropriately positioned hepatic arterial catheters. The device is also indicated for HCC patients with partial or branch portal vein thrombosis/occlusion, when clinical evaluation warrants the treatment. The effectiveness of this device for this use has not been demonstrated.

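### A hepatocellular carcinoma test for new liver nodules stands beside an any-new-lesion rule in a colorectal trial with no stated precedence; the progression reference, target-lesion cap, scan interval and survival origin also need reconciling

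*Combined protocol and SAP*

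**What the plan says.** Inclusion criterion 3.1.2 requires "Histological or cytological confirmation of colorectal cancer with metastasis to the liver".

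**New lesions.** Section 11.23 introduces concepts taken from mRECIST for HCC and then states: "A newly detected hepatic nodule will be classified as HCC, and therefore will be declared as evidence of progression". The conditions are a longest diameter of at least 1 cm and arterial hypervascularity with washout. A nodule over 1 cm without that pattern qualifies after at least 1 cm of growth on later scans, and progression is then dated to first detection. Appendix IV.C repeats the test: an atypical nodule "can be diagnosed as hepatocellular carcinoma if there is at least 1 cm internal growth on subsequent scans". Section 11.22, by contrast, lists as PD "Appearance of 1 or more new lesions and/or unequivocal progression of existing nontarget lesions". Appendix IV.A adds to its target-lesion PD rule "or the appearance of one or more new lesions", and its best-response table scores any new lesion as PD. Section 11.24 joins the parts: "In mRECIST for HCC, identical to conventional RECIST v1.1, overall subject response is a result of the combined assessment" of target, non-target and new lesions.

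**Progression.** Section 11.1 states: "Disease progression for this protocol is defined as meeting the mRECIST as well as iRECIST criteria detailed in appendix VI". The appendix of that number is headed "Appendix VI: TheraSpheres Prescribing Information"; the response criteria are in Appendix IV. After the end-of-treatment scan, 11.1 repeats imaging every 8-12 weeks, while the test schedule in 4.1 places tumor measurement at 3-monthly follow-up.

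**Target lesions.** Appendix IV.A allows five per organ and ten in total. Appendix IV.B allows two per organ and five in total. The mRECIST text in 11.21 and IV.C gives no cap.

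**Overall survival (OS).** Section 17.5.5 counts from randomization and plans the Kaplan-Meier median. Section 17.1 describes a single-arm study. The footnote to 2.2 sets the start of immunotherapy as the landmark in every case, and 2.2.7 asks for OS at 1 and 2 years.

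**The concern.** The HCC test answers whether a new nodule is HCC. In a patient with known colorectal liver metastases that is not the question, and a new metastasis need not show the HCC pattern. Section 11.1 makes mRECIST part of the progression definition and 17.5.3 ties ORR to mRECIST, so 11.23 is operative text. Section 11.22 limits its special recommendations to patients with HCC and cirrhosis; the 11.23 bullets carry no such limit.

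Two readers, each following a section of the protocol, can therefore score one nodule differently at the scan that fixes the 2-month ORR and DCR. The same call feeds the progression-based goals in 2.2.5, 2.2.6 and 2.2.8. For OS, the written start date is one that no patient will have. These results are meant to help inform a Phase II trial (17.3), so the rules should be settled before scans are read.

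**Working it through.** No planned sample size or precision figure rests on these rules, so there is no figure of the plan to reproduce. The check compares the texts and then scales the effect.

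**1. New liver nodule first seen at the 8-week scan**

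| Nodule | 11.22 and IV.A | 11.23 and IV.C | iRECIST (IV.B) |
|---|---|---|---|
| Under 1 cm | PD | test not met | unconfirmed progression (iUPD) |
| At least 1 cm, HCC pattern | PD | PD | iUPD |
| Over 1 cm, no HCC pattern | PD | not met until at least 1 cm of growth, then back-dated | iUPD |

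The first and third rows conflict. For example, a 1.1 cm atypical nodule must reach 1.1 + 1.0 = 2.1 cm. That cannot be shown on the scan where the nodule first appears. The conflict covers liver nodules only; new extrahepatic lesions fall under 11.22.

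**2. When growth could be seen.** The end-of-treatment visit is 8 weeks after Y90-RE (4.1, footnote 12). Under 11.1 the next routine scan falls at 8 + 8 = 16 to 8 + 12 = 20 weeks. Under the 3-monthly schedule in 4.1 it falls at about 8 + 13 = 21 weeks. Section 17.5.2 allows an optional confirmatory scan for clinical concerns.

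**3. Size of one reclassification.** Assume that all 18 patients are evaluable. One patient is 1/18 = 5.6 points. If that patient's target lesions are stable, only DCR moves; if they show partial or complete response, ORR and DCR both move. Exact (Clopper-Pearson) 95% intervals for illustrative counts:

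- DCR: 9/18 = 50.0% (26.0-74.0) against 10/18 = 55.6% (30.8-78.5)
- ORR: 3/18 = 16.7% (3.6-41.4) against 4/18 = 22.2% (6.4-47.6)

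**4. Target-lesion cap.** Assume five liver lesions of 50, 40, 30, 25 and 20 mm that become 30, 25, 29, 25 and 20 mm.

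- Two per organ: (90 - 55)/90 = 38.9% decrease, a partial response
- Five per organ: (165 - 129)/165 = 21.8% decrease, stable disease

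The sizes are invented; they show only that the cap can change a category.

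**5. OS origin.** At dose levels 1-4 the first durvalumab dose precedes Y90-RE by 2 weeks, so start of immunotherapy and first study treatment coincide. At levels -1 and -2 durvalumab follows Y90-RE, so the two origins differ.

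**The case against.** The strongest reply is that 11.23 only reports a source criterion. Its lead-in names mRECIST for HCC, its bullets say when a nodule is classified as HCC, and nothing says that other new lesions are not PD. Section 11.22, IV.A and the reference to conventional RECIST in 11.24 all lead to PD. This stands in part: a careful reader can reach PD. What remains is that HCC wording sits in operative text with no sentence saying which rule governs.

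Several stronger readings are tempting, and the documents do not support them:

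- A reader might infer that 11.23 forbids PD for any other nodule. It does not say so.
- A reader might infer that a late-qualifying nodule gets a late progression date. Section 11.23 back-dates it to first detection. What is missing is whether an already recorded 2-month ORR or DCR is then revised; nodules that never qualify are not helped.
- A reader might take 11.1 to require mRECIST and iRECIST progression jointly. The 2.2 footnote and 17.5.2 point to parallel reporting, so 11.1 needs only to be aligned with them.
- A reader might infer that DCR has no criterion because 17.5.4 names none. Section 17.5.3 labels complete response, partial response and stable disease as mRECIST; a cross-reference is enough.
- A reader might scale the effect to the lower enrolment of 12 in 1.4.7. Sections 17.1 and 17.3 target 18, and 17.5.3 replaces non-evaluable subjects.

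It is also fair that the 2.2 footnote already supplies an OS origin and that a Kaplan-Meier curve yields 1- and 2-year values. Section 17.5.5 still contradicts the first and omits the second.

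**Conclusion.** The point holds as a conflict between rules with no stated precedence, together with wording errors in linked sections. A new liver nodule that is under 1 cm, or over 1 cm without the HCC pattern, can be PD or non-PD at the 8-week scan depending on the section followed. Each such patient moves DCR, or ORR and DCR for a target-lesion responder, by 5.6 points if all 18 are evaluable. How many patients are affected is unknown and may be zero, and one patient matters less than sampling error.

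A reader might infer that the trial's conclusions are at risk. They are not: these endpoints are secondary and descriptive, 17.5 treats all results as exploratory, and the MTD, the dose-limiting toxicity rules and the sample size do not depend on them. The OS origin in 17.5.5 and the appendix reference in 11.1 are plain errors. The change is worth making because it is cheap and is best made before scans are read.

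**What to change.** - **11.23 and IV.C:** state that the HCC nodule test does not apply to colorectal metastases and that 11.22 governs. Any unequivocal new lesion is PD under mRECIST, and iUPD pending confirmation under iRECIST. Label this as an adaptation of mRECIST limited to new lesions. If back-dating is kept for equivocal nodules, state that it also revises the 2-month ORR and DCR.
- **11.1:** state that mRECIST and iRECIST progression are determined and dated separately, and cite Appendix IV.
- **11.1 and 4.1:** reconcile the follow-up scan interval.
- **Appendix IV and 11.21:** state one target-lesion cap for all criteria.
- **17.5.4:** add a cross-reference to the mRECIST categories in 17.5.3.
- **17.5.5:** replace randomization with the 2.2 footnote origin or with first study treatment, and reconcile the two for levels -1 and -2. Report Kaplan-Meier OS at 1 and 2 years with 95% confidence intervals, alongside the median.

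The cost is wording and an update of the response form, with no extra scans. The adapted rule departs from published mRECIST and must be reported as such. DCR may be slightly lower, and an ambiguous nodule may be called PD early; the word unequivocal and the parallel iRECIST reading limit this. If back-dated PD revises the 2-month result, that result is final for a patient with an equivocal nodule only after the next scan.

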11.24 Overall Response Assessment

In mRECIST for HCC, identical to conventional RECIST v1.1, overall subject response is a result of the combined assessment of both intra- and extrahepatic target lesions, non-target lesions, and new lesions.

12.0 Descriptive Factors

Baseline characteristics pertaining to the patient as well as the tumor would be reported. With respect to the patient, this would include but not limited to age, sex, the performance status, lines of prior therapy and types of previous therapies received. We would also report on pharmacogenomics assessed on each patient. With respect to the tumor, we would obtain information including but not limited to mutational status (RAS/RAF), mismatch repair status (or microsatellite instability), tumor mutation burden (based on NGS assay), RNA-seq and PD-L1/PD-1 expression.

13.0 Treatment/Follow-up Decision at Evaluation of Patient

Reason Off Treatment (from the Off-Treatment Form)	Go to CFU, SFU, or end folder rollout
1 = Treatment (Intervention) Completed Per Protocol Criteria	CFU
2 = Patient Withdrawal/Refusal After Beginning Protocol Therapy (Intervention)	CFU/SFU/No follow-up
3 = Adverse Events/Side Effects/Complications	CFU
4 = Disease Progression, Relapse During Active Treatment (Intervention)	SFU
5 = Alternative Therapy	SFU/No follow-up
6 = Patient Off-Treatment (Intervention) For Other Complicating Disease	SFU
7 = Death On Study	No follow-up
8 = Other	SFU/SFU/No follow-up
10 = Disease Progression Before Active Treatment (Intervention)	No follow-up
24 = Patient Withdrawal/Refusal Prior To Beginning Protocol Therapy (Intervention)	No follow-up

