4.2 Survival Follow-up

	Survival Follow-up				
	q. 3 months until PD	At PD	After PD q. 3 months	Death	New Primary
Survival Follow-up	X	X	X	X	At each occurrence

1. If a patient is still alive 5 years after registration, no further follow-up is required.

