13.3 Off protocol treatment

Patients who go off protocol treatment for reasons other than PD will go to the event-monitoring phase per Section 4.0.

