17.5.3 Overall Response Rate

Overall response rate is defined as the proportion of evaluable patients that have achieved a complete response or partial response using mRECIST evaluation criteria. ORR will be evaluated at 2 months post-Y90RE treatment (\pm 5 business days).

ORR will be analyzed descriptively as a point estimate with a 95% confidence interval.

Results will be reported consistent with RECIST v1.1 (Appendix A.9).

An “evaluable subject” for the purpose of evaluation of the combinatorial therapy is one who receives both Y90-radioembolization and at least 1 dose of durvalumab.

Subjects who do not receive Y90-RE or received only a single incomplete dose of immunotherapy (i.e., allergic reaction), are considered non-evaluable for assessment of efficacy. These subjects would be replaced for the proposed sample size of 18.

All subjects included in the study must be assessed for response to treatment, even if there are major protocol treatment deviations or if they are ineligible.

Each subject will be assigned one of the following categories: 1) complete response (mRECIST), 2) partial response (mRECIST), 3) stable disease (mRECIST), 4) progressive disease (mRECIST), 5) early death from malignant disease, 6) early death from toxicity, 7) early death because of other cause, or 9) unknown (not assessable, insufficient data).

Category 4 (protocol specific definition): includes clinical progression as determined by the principal investigator and confirmed by the independent data and safety monitoring committee (DSMC).

Category 5 (protocol specific definition): death from malignant disease as determined by the principal investigator and confirmed by the independent data and safety monitoring committee (DSMC).

Category 6 (protocol specific definition): death from toxicity as determined by the principal investigator and confirmed by the independent data and safety monitoring committee (DSMC).

Category 7 (protocol specific definition): includes death not meeting categories 5 or 6, or death defined as not otherwise specified.

Category 9 (protocol specific definition): includes subjects who did not receive radioembolization, or who did not receive at least 1 complete infusion of durvalumab, or who did not undergo follow-up imaging (other than for clinical progression, toxicity, or death), or subjects who are lost to follow-up.

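### The off-treatment table in 13.0 conflicts with 11.1, 1.4.6 and 17.5.3 on follow-up of patients who stop without progression or withdrawn consent

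*Combined protocol and SAP*

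**What the plan says.** The table in 13.0 assigns each off-treatment reason to clinical follow-up (CFU), survival follow-up (SFU) or no follow-up.

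- Code 6, "6 = Patient Off-Treatment (Intervention) For Other Complicating Disease", goes to SFU.
- Code 5, "5 = Alternative Therapy", goes to SFU or no follow-up.
- Code 8, other reasons, reads "SFU/SFU/No follow-up".
- Code 3, adverse events, goes to CFU.
- Progression (codes 4 and 10) and patient withdrawal or refusal (codes 2 and 24) have codes of their own.

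The test schedule in 4.1 places tumor measurement at screening, at the end-of-treatment (EoT) visit and in the CFU column. Footnote 12 fixes the EoT visit at 8 weeks after Y90-RE. The survival follow-up table in 4.2 has contact "q. 3 months until PD", at progression, three-monthly after progression and at death. It has no imaging row.

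Other sections ask for more:

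- 11.1, on scans after the EoT visit: "It will then continue every 8-12 weeks per physician discretion until disease progression is confirmed or withdrawn of consent".
- 1.4.6 keeps PFS and OS follow-up after the EoT visit even though patients will be starting another regimen.
- 17.5.3 requires all included subjects to be assessed for response, even after major treatment deviations.
- 13.3: "Patients who go off protocol treatment for reasons other than PD will go to the event-monitoring phase per Section 4.0".

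**The concern.** Patients under codes 5, 6 and 8 have neither progressed nor withdrawn consent under the table's own coding. The table still takes them off the recurring schedule that includes tumor measurement. For codes 5 and 8 it also allows survival tracking to stop, and nothing says when. Whether a patient keeps being scanned then depends on the reason written on the Off-Treatment Form.

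Starting another therapy or developing a complicating illness is plausibly related to prognosis, although the documents neither say so nor quantify it. If such patients leave observation, three things are at stake:

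- PFS and duration of response would rest on contact without scheduled scans.
- Under 17.5.5, OS is censored at the date last known alive. For a patient given no follow-up, that date is set by the decision to stop.
- A treated patient who stops before week 8 may or may not have the scan on which response at 2 months depends.

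**Working it through.** The plan states no figure for this point, so the check is mainly a comparison of sections.

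**Step 1: destinations against the stated requirements.**

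| Code | Destination in 13.0 | Scheduled imaging after the EoT visit | Survival tracking |
|---|---|---|---|
| 3 (adverse events) | CFU | Yes (4.1) | Yes |
| 6 (complicating disease) | SFU | None in 4.2 | Yes |
| 5 (alternative therapy) | SFU or none | None in 4.2 | Only if SFU is chosen |
| 8 (other) | SFU, SFU or none | None in 4.2 | Only if SFU is chosen |

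Section 11.1 gives two reasons to stop scanning: confirmed progression and withdrawn consent. Codes 5, 6 and 8 record neither. The table therefore conflicts with 11.1 on imaging for all three codes. For codes 5 and 8 it also conflicts with 1.4.6 on OS.

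**Step 2: does 13.3 settle it?** It covers every discontinuation other than progression, so it includes codes 5, 6 and 8. It points to an event-monitoring phase in Section 4.0, but Section 4.0 contains only screening, active monitoring (with the EoT visit and clinical follow-up) and survival follow-up. The reader cannot tell whether imaging is meant.

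**Step 3: what happens to the response rate.** A patient who received Y90-RE and at least one durvalumab dose is evaluable under 17.5.3. Category 9 in that section includes subjects "who did not undergo follow-up imaging (other than for clinical progression, toxicity, or death"). Section 17.5.3 adopts the Appendix IV A.9 reporting rules, under which categories 4 to 9 count as failure to respond. A missed week-8 scan thus becomes a non-response for ORR. Section 17.5.4 states no such rule for DCR.

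**Step 4: size per patient.** With *n* = 18 (1.4.7) and *k* patients unassessed, the gap between the worst and best case for a proportion is *k*/18:

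- *k* = 1: 1/18 = 5.6 percentage points
- *k* = 2: 2/18 = 11.1 percentage points

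For illustration, assume 4 observed responders. Counting the unassessed as failures gives 4/18 = 22.2% (exact 95% CI 6.4% to 47.6%). If the unassessed had all been responders, ORR would be 5/18 = 27.8% for *k* = 1 and 6/18 = 33.3% for *k* = 2. Both *k* and the 4 responders are assumptions.

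**Step 5: scale of a possible OS bias, under assumptions.** Take exponential survival with the 10.6-month median quoted in 1.2.2 for a retrospective glass-microsphere series, so λ = ln 2/10.6. Suppose 10% of patients are censored at 2 months and their later hazard is HR times that of the rest. Kaplan-Meier then estimates exp(−24λ) = 20.8% at 2 years. The true value is 0.9·exp(−24λ) + 0.1·exp(−2λ)·exp(−22λ·HR):

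- HR 0.5: 23.0%
- HR 2: 19.2%
- HR 3: 18.9%
- HR 5: 18.7%

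The gap is about 1.6 to 2.2 percentage points in either direction. An approximate 95% half-width for 20.8% with 18 patients is 1.96·√(0.208·0.792/18), about 19 points.

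**The case against.** The strongest reply is that this is an editing conflict and not a mechanism that loses endpoints. Much of that stands.

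- **SFU is more than vital status.** A reader might infer that these patients have survival-only follow-up and that PFS is lost. Section 4.2 does not support that: it schedules contact every three months until progression and at progression. PFS ascertainment is weaker without scheduled scans, but it is not abolished.
- **OS is kept for code 6.** OS is exposed only for codes 5 and 8, and only if no follow-up is chosen.
- **Code 8 may be a slip.** The repeated SFU entry looks like an error for the CFU/SFU/No follow-up entry of code 2.
- **The week-8 visit is its own column in 4.1.** It belongs to neither CFU nor SFU, and 17.2 has patients observed for at least 8 weeks after Y90-RE. Loss of that scan is therefore a risk created by unclear text, not a certainty.
- **Failure-counting in A.9 concerns the response rate.** A reader might extend it to DCR, but the documents do not.
- **The 10% loss in 1.4.6 is not a rate for these codes.** It is general loss after enrollment, used for the dose-escalation count. Reading it as an 11-point understatement of ORR, or as a demonstrated OS bias, is unsupported. The hazard ratios in step 5 are assumed, and the resulting gap is small beside the sampling error.

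The objection does not remove the conflict. The table is the instruction staff would use to route a patient, and for codes 5, 6 and 8 it departs from 11.1 and, for codes 5 and 8, can end the OS follow-up that 1.4.6 retains.

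**Conclusion.** The point holds as an unreconciled contradiction with a practical consequence. Followed as written, 13.0 takes non-progressed, consenting patients off scheduled imaging and permits survival tracking to end without a condition for codes 5 and 8. This weakens PFS and duration-of-response ascertainment, allows potentially informative OS censoring for those two codes, and leaves the week-8 assessment unclear for treated patients who stop early.

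The overall size is unknown because no rate is given for these reasons. Per affected patient, the bound is 5.6 percentage points on a proportion of 18. That bound assumes all 18 are in the denominator and that the patient's unobserved outcome differs from the one assigned.

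The affected efficacy endpoints are secondary, and 17.5 describes the analyses as exploratory. Priority is modest.

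**What to change.** - In the 13.0 table, route treated patients under codes 5, 6 and 8 so that they keep the week-8 EoT assessment, then imaging under 11.1 until progression, then survival follow-up. If code 8 is a typing slip, correct it in the same edit.
- Among treated patients, limit the no-follow-up destination to death or withdrawal of consent to follow-up.
- Reword 13.3 to name a phase that exists in Section 4.0 and agrees with the revised table.

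This means changing a few table cells and one sentence. The visits and scans are already planned under 4.1 and 11.1. The downside is continued follow-up of perhaps one or two patients, a guess given that the documents state no rate.
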